1 DOCUMENT CHANGE HISTORY

Version number	Version date	Author	Description of change(s)
1.0	22dec2019	[name]	Original protocol
1.1	02jan2020	[name]	Changes to Inclusion Criteria, section 5.2.3: changed minimum age to 42 yrs; added minimum refractive astigmatism of - 0.75DC. Expanded section 5.4 to provide more detail regarding assessments to be conducted at each study visit. Other minor edits following sponsor review.
1.2	10feb2020	[name]	Administrative changes
1.3	11mar2020	[name]	Added Health Canada DIN for Biofinity Toric Multifocal (Table 1) and clarified objectives and visit windows (Table 3).
1.4	16apr2020	[name]	Several minor corrections to improve consistency and aid clarifications throughout plus, specifically: corrected address for site A.; removed site F who are now unable to participate; updated and clarified Section 5.3.5; corrected procedure for determining ocular dominance, Section 5.4.1.
1.5	19may2020	[name]	Removed the note under Table 1 “* Study will not commence until the Health Canada license has been assigned to Biofinity Toric Multifocal.” because the HC license has now been approved.
1.6	14sep2020	[name]	Minor text updates throughout to reflect the change that CORE will be the only research site that seeks ethics approval through the Office of Research Ethics (ORE) at the University of Waterloo, for all other sites this study will be reviewed by either the Sterling Institutional Review Board (IRB) or the Health Research Ethics Board of Alberta – Clinical Trials Committee (HREBA-CTC).

1.7	21dec2020	[name]	Two new clinical sites were added ([name] and [name]) and one clinical site which was never initiated was removed ([name]) Other administrative changes
-----	-----------	---------------------	--

Table of contents

1	Document change history	4
2	Introduction.....	10
3	Objectives.....	10
4	Hypothesis.....	10
5	Materials and methods	10
5.1	Study design	10
5.1.1	Overall design	10
5.1.2	Randomization	11
5.1.3	Masking.....	11
5.2	Study population	11
5.2.1	Sample size calculation.....	11
5.2.2	Number of participants	12
5.2.3	Inclusion and exclusion criteria.....	13
5.3	Study materials	14
5.3.1	Lenses	14
5.3.2	Lens care system	15
5.3.3	Other products	15
5.3.4	Rewetting drops	15
5.3.5	Ordering study products	15
5.3.6	Disposing of study products	16
5.3.7	Product accountability	16
5.4	Scheduled and unscheduled visits	16
5.4.1	VISIT 0, Screening VISIT	17

2 INTRODUCTION

Multifocal contact lenses provide correction for vision at near as well as in the distance. This segment of the contact lens market has been slowly growing as more products become available. In the past year, two monthly replacement, multifocal contact lenses have come to market that also correct the astigmatism component of a prescription.

CooperVision are interested in comparing their contact lens (Biofinity Toric Multifocal) with a competitor lens (Ultra Multifocal for Astigmatism, Bausch & Lomb). Of particular interest is the comparison of handling the lens to insert onto the eye. A previous study sponsored by CooperVision compared the non-multifocal lenses of these lens brand families, and showed that the Biofinity Toric lens was easier to insert than the Ultra for Astigmatism lens. Ease of handling a lens for insertion is arguably more critical in a presbyopic population who require specific prescription for seeing well up close.

3 OBJECTIVES

The objective of the study is to compare the handling and performance of Biofinity Toric Multifocal to Ultra Multifocal for Astigmatism.

The primary outcome variable for this study is:

1. Subjective at-home ratings of 'Lens handling for insertion', using a 0-10 scale, collected on Day 28.

4 HYPOTHESIS

The null hypothesis is that there will be no difference between the subjective at-home ratings of 'Lens handling for insertion', collected on day 28 for each lens type.

5 MATERIALS AND METHODS

5.1 STUDY DESIGN

5.1.1 OVERALL DESIGN

This is a prospective, randomized, participant masked, crossover, bilateral dispensing study conducted at CORE and seven other clinical practice sites in Canada and the USA. Each lens type will be worn for approximately one month. The lens prescription of each lens type will be optimized after 3-7 days before the one month wear period.

5.1.2 RANDOMIZATION

A randomization schedule will be generated using a web-based program: (www.randomization.com). The final study randomization schedule will be generated by CORE's Database Administrator and provided to the research assistants at each site for the study.

5.1.3 MASKING

Participants will be masked to the lens type they are wearing during the study. Foils will not be visible to participants when the lenses are removed from the blister packs and information specifying which lens is being worn will not be shared with the participant.

It is not possible for the study investigators to be masked because of the need to follow the specific lens fitting guide during the lens prescription optimization visit (visits 1-1 and 2-1).

5.2 STUDY POPULATION

5.2.1 SAMPLE SIZE CALCULATION

The sample size was calculated using the end of month subjective ratings for 'lens handling for insertion' from a previous study.

In order to detect a mean difference of 0.7 units on the 0 to 10 scale for the end of month ratings of 'lens handling for insertion', using a standard deviation of 1.7 with 80% power and alpha 0.05 in a two-tailed t-test, a minimum sample size of 49 participants is recommended. To account for dropout, up to 60 participants may be randomized and dispensed with study product in total, with the target of at least 49 completing the study.

[figure not shown]

Figure 1: Sample size calculation graph

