5.4.6 VISIT 1-1, LENS POWER OPTIMIZATION PAIR #1

This visit will occur 3-7 days after the lenses were dispensed at visit 1-0. Participants will be asked to insert lenses at least 2 hours prior to the visit.

The contact lens power optimization procedures to be performed are outlined below:

1. Confirm participant's health and medications are unchanged.

2. [REDACTED]

3. [REDACTED]

4. [REDACTED]

[REDACTED]

6. [REDACTED]

[REDACTED]

[REDACTED]

[REDACTED]

11. If final lenses were determined today and are available for dispense, provide and explain to participant the subjective at-home rating forms to be completed on Days 7, 14 and 28 (Note: Day 1 is the day after the dispensing visit). Fill in the days and dates on these forms. Explain the ratings will include:

a. [REDACTED]

c. Ease of lens handling for insertion onto eyes (0 – 10 integer scale);

d. [REDACTED]

- f. [REDACTED]

12. The participant will be scheduled/reminder to return for Visit 1-2 having worn their study contact lenses for at least 2-hours.

NOTE: If any power changes are required and the new power lenses are not available on site to assess, complete a lens order form (on CRF 5). When the lenses arrive on site, schedule an additional optimization visit to assess and dispense the new lens powers ordered. If new lenses need to be ordered, participants should wear their habitual lenses in the mean time and attend the next optimization visit wearing spectacles.

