12 STATISTICAL ANALYSIS AND DATA MANAGEMENT

12.1 STATISTICAL ANALYSIS

All data will be analyzed by CORE at the University of Waterloo. Unmasked data analysis will be conducted using Statistica 10, Statsoft or other suitable software. Descriptive statistics will be provided on demographic data (age, gender, refractive error distribution, etc.). Table 7 lists the primary and other outcome variables and anticipated statistical procedures.

Visual acuity results will be converted to LogMAR for analysis purposes.

Comparisons will be made between the study lenses for the variables measured at the 1 month visits. Additionally the subjective ratings completed on days 7, 14 and 28 of each phase will be compared. A binomial test will be used to analyze the results for the count data of subjective preferences and experience responses. Where relevant, the number of “neither agree or disagree” responses will be evenly distributed to the two options on the basis they would be equally likely to choose either.

Because of the phenomenon of binocular summation, binocular visual acuity will be analysed, not right eye data. For other variables, such as lens fit, the right eye data will be reported and compared.

Where appropriate, such as for lens orientation, data may be presented as both mean and as counts by 'bucket' groups.

Table 7: Statistical procedures

Variable	Analysis	Statistical test
Ratings: Likert & Preference	Comparison between study days and/or between contact lenses per time point.	Freidman ANOVA Wilcoxon matched pairs test
Ratings: numerical ratings Biomicroscopy	Comparison between study days and/or between contact lenses per time point.	Freidman ANOVA Wilcoxon matched pairs test RMANOVA
Demographics Lens fit variables	Descriptive stats	One or more: mean, median*, mode, standard deviation, minimum, maximum, frequency count

* For non-parametric data only

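### Does leaving three tests open for the Day 28 insertion rating put the stated 80% power or the 5% alpha at risk?

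*Combined protocol and SAP*

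**What the plan says.** Section 3 names one primary outcome: "Subjective at-home ratings of 'Lens handling for insertion', using a 0-10 scale, collected on Day 28". Section 4 states a single null hypothesis, of no lens difference in that rating on that day. Section 5.4.6 describes the item as "Ease of lens handling for insertion onto eyes (0 – 10 integer scale", so the data are bounded whole numbers. The design (Section 5.1.1) is a crossover, so each participant rates both lenses.

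The sample size in Section 5.2.1 begins "In order to detect a mean difference of 0.7 units on the 0 to 10 scale", continues "using a standard deviation of 1.7 with 80% power and alpha 0.05 in a two-tailed t-test", and concludes that "a minimum sample size of 49 participants is recommended". It then adds: "To account for dropout, up to 60 participants may be randomized and dispensed with study product in total".

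Section 12.1 says that "Table 7 lists the primary and other outcome variables and anticipated statistical procedures". The row for numerical ratings covers comparisons between study days, between lenses at each time point, or both, and its test column reads "Freidman ANOVA Wilcoxon matched pairs test RMANOVA". No t-test appears by name, no test is singled out for the primary outcome, and the analysis is described as unmasked.

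**The concern.** The sample size is tied to one test, and the analysis section offers three others. If the test that decides the primary hypothesis is weaker than the t-test, 49 completers do not give 80% power. Friedman's test with two conditions is a sign test, which discards the size of each difference. If the test is chosen after unmasked results have been seen, the same hypothesis has several possible p-values, and reporting the most favourable one takes the type I error above 5%. In a sponsor's comparison with a named competitor on one subjective rating, a result that depended on the choice of test would be open to challenge.

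**Working it through.** **Inputs.** Section 5.2.1: difference 0.7, SD 1.7, two-sided alpha 0.05, power 80%, n = 49. Section 5.4.6: integer scale from 0 to 10. Assumption: 1.7 is the SD of the within-participant difference; the text does not say so, and Figure 1 is not shown.

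**1. Reproducing 49.** For a paired t-test the non-centrality is (0.7/1.7) × √n. At n = 49 it is 0.4118 × 7 = 2.88 on 48 degrees of freedom.
- Exact non-central t: 79.8% power at n = 48 and 80.6% at n = 49, so 49 is the smallest n that reaches 80%.
- Normal approximation: (1.7 × (1.960 + 0.842)/0.7)² = 46.3, hence 47.
- Two independent groups: 2 × 46.3 = 92.6, hence 93 per arm.

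Only the exact paired calculation gives 49, which supports the reading of the SD.

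**2. Repeated-measures ANOVA.** With two lenses on one day, F = t² on 1 and 48 degrees of freedom. The p-value is the same and power is 80.6%.

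**3. Power of the listed tests by simulation** (n = 49, 20,000 trials per scenario, true difference about 0.7):

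| Distribution of differences | SD | Paired t / two-lens ANOVA | Wilcoxon | Two-lens Friedman |
|---|---|---|---|---|
| Normal | 1.70 | 81.1% | 79.2% | 61.0% |
| Rounded to integers | 1.73 | 79.7% | 79.0% | 69.7% |
| Integers near the top of the scale | 1.82 | 77.2% | 76.2% | 68.3% |

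The t-test also falls in the lower rows because the SD there is larger than 1.7: rounding alone gives √(1.7² + 1/12) = 1.72. Within each row Wilcoxon costs 0.7 to 1.9 points. Its asymptotic efficiency of 3/π implies 49/0.955 = 51.3 completers for equal power under normality, about two to three more.

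Hand check of the Friedman figure under normality: P(difference > 0) = Φ(0.4118) = 0.660. The standardised mean is (2 × 0.6598 − 1) × 7 = 2.24 with SD 2√(0.6598 × 0.3402) = 0.948. Power is about Φ((2.237 − 1.960)/0.948) = Φ(0.29), or 61%. On the integer scale small differences become ties and drop out, which lifts the figure to about 70%.

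**4. Type I error.** Each test alone rejects in 4.7% to 5.1% of null trials. Reporting the smaller of the t and Wilcoxon p-values gives 5.5% to 5.8%. Reporting the smallest of all three gives 7.3% to 7.8%.

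**5. How often the choice matters at the planned effect.** The share of trials in which t and Wilcoxon disagree is 2 × P(either rejects) − P(t rejects) − P(Wilcoxon rejects).
- Normal: 2 × 0.8258 − 0.8108 − 0.7916 = 4.9%.
- Integer: 2 × 0.8079 − 0.7971 − 0.7895 = 2.9%.

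**6. Which test belongs to which comparison.** Table 7 names two kinds of comparison. There are three rating days (7, 14 and 28) and two lenses. Friedman is the usual rank test for three or more related conditions, and Wilcoxon matched pairs is the usual one for two. The table gives days before lenses and Friedman before Wilcoxon, in the same order. If Friedman were meant for the two lenses, Wilcoxon would have no separate purpose. The natural candidates for the Day 28 lens contrast are therefore Wilcoxon and two-lens repeated-measures ANOVA.

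**The case for a change.** The table does not assign tests to comparisons, so Friedman on two lenses is not excluded in writing. With it included, the three tests disagree on significance in about 25% of trials at the planned effect under normality, and 16% on the integer scale. Repeated-measures ANOVA is also open to interpretation. A lens main effect pooled over days 7, 14 and 28 would have 83% to 97% power if the difference were 0.7 on every day, but only 31% to 48% if it grew from 0 through 0.35 to 0.7 (correlations between days of 0.9 to 0.3, assumed). Choosing between the pooled test and the Day 28 test gives 6.1% to 8.1% type I error. Unmasked analysis removes one safeguard against such choices, and naming one test would cost only wording.

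What stands is that the deciding test is not written down. The rest is weaker. A pooled main effect does not test the hypothesis in Section 4, which is confined to Day 28, and Table 7 compares the lenses at each time point. The disagreement rates of 16% and 25% come mostly from Friedman; without it they are about 3% and 5%. The inflation figures describe an analyst who runs every test and reports the best, which no section plans. Unmasked analysis does not itself raise the error rate of any test, and the rating comes from participants who are masked to lens type (Section 5.1.3).

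**Conclusion.** No change is called for. This is an unstated detail that an analyst following the plan fills sensibly. On the natural reading the planned 80% becomes 79% to 81% under the planning SD, and the worst effect of choosing between the two plausible tests is a type I error of about 5.8%. Because 49 is a minimum and up to 60 may be randomized, the one or two points that Wilcoxon can cost are within the recruitment margin.

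Power near 61% to 70% and alpha near 7% to 8% are worst cases outside what the plan describes. Preferring a parametric test or Wilcoxon for a bounded integer rating is a matter on which statisticians reasonably differ, and either choice supports the conclusion.

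This rests on 1.7 being the SD of paired differences, which the exact match at 49 supports; on the simulated shapes being reasonable for this scale; and on Friedman being meant for comparisons across the three rating days.

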5.2.2 NUMBER OF PARTICIPANTS

Participants will be recruited using site records, databases and advertising materials (eg. posters, email scripts) approved by the relevant research ethics review board. All initial individual-targeted recruitment activities, such as any direct mailing of recruitment scripts, will be conducted by practice staff that are not directly involved in conducting the research. This separation will reduce any undue influence of the optometrist-patient relationship. This process will also eliminate opportunity for the investigator to access personal health information before any consent for disclosure is provided by the potential participant.

It is anticipated that up to 80 potential participants may attend a Screening visit and up to 60 participants may be randomized and dispensed with study products, with a target of 49 completing the study. Informed consent will be obtained for all participants prior to their enrolment in the study (Appendix 1).

5.2.3 INCLUSION AND EXCLUSION CRITERIA

A person is eligible for inclusion in the study if he/she:

1. Is at least 42 years of age and has full legal capacity to volunteer;
2. Has read and signed an information consent letter;
3. Self reports having a full eye examination in the previous two years;
4. Anticipates being able to wear the study lenses for at least 8 hours a day, 5 days a week;
5. Is willing and able to follow instructions and maintain the appointment schedule;
6. Habitually wears soft contact lens for the past 3 months minimum;
7. Has refractive astigmatism of at least -0.75DC;
8. Is presbyopic and requires a reading addition of at least +0.75D;
9. Can be fit and achieve binocular distance vision of at least 20/30 Snellen (or +0.20 logMAR) which participants also deem to be 'acceptable', with the available study lens parameters (sphere +4 to -6; cylinder -0.75 to -1.75DC; near addition +0.75 to +2.50).

A person will be excluded from the study if he/she:

1. Is participating in any concurrent clinical or research study;
2. Habitually wears one of the study contact lenses;
3. Has any known active* ocular disease and/or infection;
4. Has a systemic condition that in the opinion of the investigator may affect a study outcome variable;
5. Is using any systemic or topical medications that in the opinion of the investigator may affect contact lens wear or a study outcome variable;
6. Has known sensitivity to the diagnostic sodium fluorescein and/or the care product Opti-Free PureMoist being used in the study;
7. Self-reports as pregnant, lactating or planning a pregnancy at the time of enrolment;
8. Has undergone refractive error surgery.

* For the purposes of this study, active ocular disease is defined as infection or inflammation which requires therapeutic treatment. Mild (i.e. not considered clinically relevant) lid abnormalities (blepharitis, meibomian gland dysfunction, papillae), corneal and conjunctival staining and dry eye are not considered active ocular disease. Neovascularization and corneal scars are the result of previous hypoxia, infection or inflammation and are therefore not active.

Age ≥ 42 years is an inclusion criteria because presbyopia is unlikely in persons aged < 42 years and, if present, may not be due solely to presbyopic changes representative of the wider population.

Pregnant and lactating women are not being excluded from the study due to safety concerns but due to fluctuations in refractive error, accommodation and/ or visual acuity that occur secondary to systemic hormonal changes. It has further been shown that pregnancy could impact tear production, which could impact dry eye symptoms. Such fluctuations could affect data, thereby negatively affecting study data integrity.

5.3 STUDY MATERIALS

CORE’s Research Assistants will coordinate with all sites (including CORE) to provide them with the study paperwork and study products, as required. This will include participant informed consent letters and study forms, contact lenses and lens care product.

5.3.1 LENSES

The table below lists the contact lens details and the available lens parameters.

Table 1: Lens characteristics & parameter to be used

Lens	Biofinity Toric Multifocal	Ultra Multifocal for Astigmatism
Manufacturer	CooperVision	Bausch & Lomb
Material	comfilcon A	samfilcon A
HC licence #	70149	101686
Sphere power (D)	+4.00 to -6.00 (0.25 steps)	+4.00 to -6.00 (0.25 steps)
Cylinder power (DC)	-0.75, -1.25, -1.75	-0.75, -1.25, -1.75
Axis (degrees)	5 to 180 (5 steps)	10 to 180 (10 steps)
ADD power (D)	+1.00, +1.50, +2.00, +2.50	Low (+0.75 to +1.50), High (+1.75 to +2.50)
Base curve (mm)	8.7	8.6
Diameter (mm)	14.5	14.5

5.3.2 LENS CARE SYSTEM

The lens care system to be used by all participants is OptiFree PureMoist. Participants will be provided the package insert as an instruction guide for the (rub and rinse) care and storage of their study contact lenses.

Table 2: Lens care system

OptiFree PureMoist	
Manufacturer	Alcon
Health Canada, DIN	02420619

5.3.3 OTHER PRODUCTS

Sodium fluorescein will be used to assess corneal and conjunctival staining.

5.3.4 REWETTING DROPS

Participants will not be encouraged to use rewetting drops; however, those who habitually used rewetting drops will be allowed to continue using their normal drops. Rewetting drop use will be recorded at each visit.

5.3.5 ORDERING STUDY PRODUCTS

Study lenses: CORE will provide sites with a small trial fitting sets for Biofinity Toric Multifocal and for Ultra Multifocal for Astigmatism. Lenses from these sets will be used at the screening visit to determine overall lens centration acceptability and axis orientation. Based on these initial trials, sites will provide CORE with their lens needs for the lens fitting visit and lens dispense using the study specific product ordering form (CRF 1). CORE will order these lenses directly from CooperVision or Bausch & Lomb and then distribute these to the sites.

OptiFree PureMoist: CORE will order this lens care product directly and ship to the other sites.

CORE will reconcile and invoice the cost of all study products and shipping to CooperVision at the end of the study.

Reimbursement to practice sites for any study product expenses directly will be provided by CooperVision at the end of the study, after CORE has reconciled the invoices and the product accountability and dispensing logs.

5.3.6 DISPOSING OF STUDY PRODUCTS

At the end of the study, all sites will return all unused products to CORE, unless otherwise directed. Worn lenses will be disposed of at the sites according to local regulations.

5.3.7 PRODUCT ACCOUNTABILITY

Accountability logs must be kept by each site to include the number of contact lenses and lens care system bottles received, dispensed and returned. (where relevant). All products dispensed to participants must also be recorded in participant dispensing logs. All logs should be sent to CORE on request.

5.4 SCHEDULED AND UNSCHEDULED VISITS

This study has a minimum of 9 scheduled study visits, including the screening visit, though some visits may be scheduled concurrently on the same day. There is an option for repeated screening and lens fitting visits as needed.

A scheduled follow-up visit may only take place when the participant attends wearing the study lenses for at least two hours. If this is not the case and the participant is not experiencing any problems with the lenses, the appointment will be rescheduled, ideally within the visit window.

Visits that fall outside of the specified visit windows will be designated as protocol deviations and at the end of the study, the data collected during protocol deviations will be assessed for their suitability to be included in the analysis population. Table 3 summarizes the scheduled study visits and study codes.

Table 3: Summary of visits

Visit code	Approximate Duration	Visits
0	1.5 hr	Screening & option for fitting both
0/R1, 0/R2	As needed	Repeat Screening if needed
0-1	1.5 hr	Fitting of both lens types
0-1/R1, 0-1/R2, 0-1/R3	As needed	Repeat Fitting if needed
Phase 1		
1-0	0.5 hr	Dispense Pair #1 (day 0)
1-1, 1-1/R1, 1-1/R2	0.5 hr	Optimize Pair #1 & dispense new Pair #1 (day 3-7 from V1-0)
1-2	1.0 hr	1 month follow-up (day 29-31 from V1-1)
Phase 2		
2-0	0.5 hr	Dispense Pair #2 (day 0)
2-1, 2-1/R1, 2-1/R2	0.5 hr	Optimize Pair #2 & dispense new Pair #2 (day 3-7 from V2-0)
2-2	0.75 hr	1 month follow-up (day 29-31 from V2-1)
EXIT	0.25 hr	Exit VA, exit forms & remuneration

Participants will complete subjective ratings 'at-home' on days 7, 14 and 28 following visits 1-1 and 2-1; anticipated to take a total of 30 minutes per phase. These ratings will be returned and reviewed at visits 1-2 and 2-2 respectively.

